7.2 Exploratory analyses comparing bivalent and monovalent boost arms

For post-M6 follow-up in Part B of the study, exploratory comparisons of COVID-19 and severe COVID-19 risk between the bivalent and monovalent boost arms will consider the Full Month 6 cohort (FM6) and count events starting 14 days after the Month 6 vaccination. Because these comparisons are not between randomized arms, covariate-adjusted study-group-and-region stratified Cox models and covariate-adjusted cumulative incidence analysis approaches will be employed. The same list of covariates described above for the primary and secondary analyses will be considered. Exploratory analyses will be performed inferentially using the cumulative incidence approach, but covariate adjustment will only be made in the presence of enough failure events (because of the stability issue of the resulting estimator); details can be found in Section 11.3.

The same exploratory analyses will be repeated within people living with HIV (PLWH) and HIV-negative participants, separately.

8 Parts A+B analyses: Pre- & post-M6 stage combined

All described analyses below will start counting events after study enrolment or 13 days after the Month 6 vaccination, based on follow-up till the Month 12 visit and the Month 18 visit. Again, the Cox model approach will always use the calendar time scale and the cumulative incidence approach will always use the study time scale. These analyses will not adjust for multiple looks of the data.

8.1 Primary analysis in the full per-protocol cohort

For analyses including information from both the pre- & post-M6 stages, the primary analysis is the comparison of COVID-19 risk between the bivalent and monovalent randomized arms in the full per-protocol (FPP) analysis cohort as defined in Section 3, using 13 days after the Month 6 vaccination as the time origin and counting events starting 14 days after the Month 6 vaccination. The FPP cohort includes a subset of participants in RM6 who received the Pre-Month 6 and Month

6 vaccinations according to the protocol without any major protocol violations. When there are at least 7 severe COVID-19 cases, the same analysis will be repeated for the severe COVID-19 endpoint as a co-primary endpoint.

The same covariate-adjusted, calendar-time-based Cox proportional hazards models as described in Section 7.1 will be employed to estimate the hazard ratio (HR) between the bivalent vs. monovalent randomized arms. The same analysis will be repeated for people living with HIV (PLWH) and for HIV-negative participants, separately. The same covariate-adjusted cumulative incidence curves as described in Section 7.1 for each comparison arm will be provided.

8.2 Exploratory analyses

For follow-up including both the pre- & post-M6 stages, two categories of exploratory analyses will be considered. One refers to the exploratory comparisons of COVID-19 and severe COVID-19 between the bivalent and monovalent arms including all participants who received a Month 6 vaccination either in or outside of the randomization scheme. The other refers to the exploratory comparisons of COVID-19 and severe COVID-19 between the hybrid vs. vaccine immunity groups by Month 6 vaccination type (bivalent, monovalent or none) including all enrolled participants. Of note, these exploratory analyses may not be all performed for the primary publication of Part B data.

8.2.1 Exploratory analyses comparing bivalent and monovalent boost groups

For follow-up including both the pre- & post-M6 stages, exploratory analyses of COVID-19 and severe COVID-19 between the bivalent vs. monovalent boost groups will be performed in the full Month 6 (FM6) analysis cohort including all participants who received the Month 6 vaccination either in or outside of the randomization scheme, using Month 6 vaccination date as the time origin and counting events starting 1 day after Month 6 vaccination. Because these comparisons are not between randomized arms, covariate-adjusted study-group-and-region-stratified Cox models using calendar time-scale and covariate-adjusted cumulative incidence analysis approaches will be employed as described above for the primary and secondary analyses that compare between bivalent and monovalent groups.

The same analysis may be repeated for PLWH and for HIV-negative participants, separately. For analyses among PLWH, in addition to covariates described above, baseline CD4 counts (\leq vs. > 500 cells/mm 3) and baseline HIV viral load (detectable vs. not detectable) will be further adjusted for. For analyses among HIV-negative participants, a subset of the covariates maybe considered to avoid data sparsity, with recent SARS-CoV-2 status as the leading covariate to consider.

8.2.2 Exploratory analyses comparing hybrid and vaccine immunity groups among PLWH

For analyses including information from both the pre- & post-M6 stages, exploratory analyses of COVID-19 and severe COVID-19 between hybrid vs. vaccine immunity groups will consider two definitions of hybrid/vaccine immunity groups. The first is based on information at baseline and follows the same definition used in the Part A SAP for AG1 (Vaccine Immunity) and AG2.1 (Hybrid Immunity) and repeated below for easy reference.

1. AG1 (PLWH Vaccine Immunity; HIV+,SARS2-,2d) = PLWH; baseline SARS-CoV-2 naïve (negative for POCS, CLS, and NAAT); assigned 2 vaccinations pre-Month 6
2. AG2.1 (PLWH Hybrid Immunity; HIV+,SARS2+,1d) = PLWH; baseline POCS positive; assigned 1 vaccination pre-Month 6

The second definition of hybrid/vaccine immunity groups is based on a combination of baseline hybrid/vaccine immunity group information, Month 6 SARS-CoV-2 status and Month 6 recent SARS-CoV-2 infection status (see definitions in Section 5). Specifically, Month 6 Vaccine Immunity group includes a subset of AG1 participants who had no evidence of SARS-CoV-infection before or at Month 6 (i.e., Month 6 SARS-CoV-2 status = vaccine immunity); Month 6 Hybrid Immunity group includes a subset of AG2.1 participants who had no evidence of recent SARS-CoV-2 infection at Month 6 (i.e., Month 6 recent infection status = negative).

Comparing baseline hybrid vs. vaccine immunity groups among PLWH

For this exploratory analysis of COVID-19 and severe COVID-19 between baseline hybrid vs. vaccine immunity groups using the first definition described above, the same analysis will be repeated for three subsets of participants: 1) participants who received the monovalent Month 6 booster; 2) participants who received the bivalent Month 6 booster; and 3) participants who did not receive the Month 6 vaccination. An analysis will be performed only if there are at least 7 endpoints in a given subset of participants. These analyses seek to understand if participants' COVID-19 and severe COVID-19 risk differs between baseline hybrid and vaccine immunity groups, counting events starting 1 day after enrollment till Month 12 or Month 18 (as opposed to Month 6 in the Part A analyses). All covariates considered in the Part A analyses of hybrid vs. vaccine immunity will be considered. In addition, Month 6 vaccination will be included as a time-varying covariate using the Cox model approach. The cumulative incidence approach will not be considered for these exploratory analyses.

Comparing Month 6 hybrid vs. vaccine immunity groups among PLWH

For this exploratory analysis of COVID-19 and severe COVID-19 between Month 6 hybrid vs. vaccine immunity groups based on the 2nd definition described above, the same analysis will be repeated for two subsets of participants: 1) participants who received the monovalent Month 6 booster; and, 2) participants who received the bivalent Month 6 booster. An analysis will be performed only if there are at least 7 endpoints in a given subset of participants. These analyses seek to understand if participants' COVID-19 and severe COVID-19 risk after the Month 6 vaccination differs between hybrid and vaccine immunity groups defined at Month 6, counting events starting 14 days after the Month 6 vaccination date. All covariates considered in the Part A analyses of hybrid vs. vaccine immunity will be considered, except that the covariate values are defined at Month 6 whenever applicable. Only the Cox model approach will be considered for these analyses; the cumulative incidence approach will not be considered.

9 Summary of primary, secondary and exploratory analyses

Table 2 summarizes the target population, study endpoints, and time frame for various primary and secondary analyses. Table 3 further summarizes the same information for various exploratory

analyses.

	Primary analysis I (applicable when # COVID-19 endpoints is at least 20)
Target population	Participants randomized to monovalent or bivalent under Protocol Version 6 (RM6)
Endpoint	COVE-/CDC-based COVID-19 endpoints counted 14 days after M6 vaccination
Time frame	13 days post M6 vaccination to M12/M18 visit
	Primary analysis II (applicable when # COVID-19 endpoints is at least 20)
Target population	Full per-protocol participants randomized to monovalent or bivalent under Protocol Version 6 (FPP)
Endpoint	COVE-/CDC-based COVID-19 endpoints counted 14 days after M6 vaccination
Time frame	13 days post M6 vaccination to M12/M18 visit
	Primary analysis III (applicable when # severe endpoints is at least 7)
Target population	Participants randomized to monovalent or bivalent under Protocol Version 6 (RM6)
Endpoint	Severe COVID-19 endpoints counted 14 days after M6 vaccination
Time frame	13 days post M6 vaccination to M12/M18 visit
	Primary analysis IV (applicable when # severe endpoints is at least 7)
Target population	Full per-protocol participants randomized to monovalent or bivalent under Protocol Version 6 (FPP)
Endpoint	Severe COVID-19 endpoints counted 14 days after M6 vaccination
Time frame	13 days post M6 vaccination to M12/M18 visit
	Secondary analysis I (applicable when # COVID-19 endpoints is at least 20)
Target population	Participants randomized to monovalent or bivalent under Protocol Version 6 (RM6)
Endpoint	COVE-/CDC-based COVID-19 endpoints counted 1 day after M6 vaccination
Time frame	M6 vaccination to M12/M18 visit
	Secondary analysis II (applicable when # severe endpoints is at least 7)
Target population	Participants randomized to monovalent or bivalent under Protocol Version 6 (RM6)
Endpoint	Severe COVID-19 endpoints counted 1 day after M6 vaccination
Time frame	M6 vaccination to M12/M18 visit
	Secondary analysis III
Target population	PLWH/PLWoH randomized to monovalent or bivalent under Protocol Version 6 (RM6)
Endpoint	COVE-/CDC-based/Severe (when applicable) COVID-19 endpoints counted 14 days after M6 vaccination
Time frame	13 days post M6 vaccination to M12/M18 visit
	Secondary analysis IV
Target population	PLWH/PLWoH randomized to monovalent or bivalent under Protocol Version 6 (RM6)
Endpoint	COVE-/CDC-based/Severe (when applicable) COVID-19 endpoints counted 1 day after M6 vaccination
Time frame	M6 vaccination to M12/M18 visit
	Secondary analysis V
Target population	Full per-protocol PLWH/PLWoH randomized to monovalent or bivalent under Protocol Version 6 (FPP)
Endpoint	COVE-/CDC-based/Severe (when applicable) COVID-19 endpoints counted 14 days after M6 vaccination
Time frame	13 days post M6 vaccination to M12/M18 visit

Table 2: Summary of target population and study endpoints for primary and secondary analyses. All analyses compare the bivalent vs. monovalent Month 6 boost arms.

10 Parameters of interest to estimate

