***Comparing the effectiveness of a hybrid immunity regimen with vaccine-induced immunity***

In addition to immunocompromise, prior SARS-CoV-2 infection has been underexamined in vaccine trials in terms of its impact on vaccine-associated immunity. It is unclear if people who have a history of past SARS-CoV-2 infection require the same vaccination regimen to achieve robust immunity as people who

are infection naïve. This is especially relevant in sub-Saharan Africa where many areas likely have SARS-CoV-2 antibody seroprevalence in excess of 85% (48, 49). There is now significant evidence suggesting that natural infection may prime the immune system, like a vaccination, and synergistically enhance immunity when a vaccine is later administered (50). This has been termed “hybrid immunity” because it is a combination of natural immunity (derived from infection) and vaccine-induced immunity. Numerous observational studies have shown that previously infected individuals who are subsequently vaccinated demonstrate a particularly vigorous immune response, even after just one dose of mRNA vaccine (51-56). In one study, a single dose of mRNA vaccine given to previously infected individuals boosted neutralizing titers against multiple strains of SARS-CoV-2 (and even SARS-CoV-1) by up to 1,000 times above those measured prior to the vaccination (52). Large prospective studies like this trial are needed to assess hybrid immunity compared to vaccine-only immunity to inform our vaccination strategies in a world now where most people have been previously infected. In addition, the post-Month 6 dose follow up in this trial will also provide information on whether individuals with hybrid versus vaccine-only immunity have different responses to the bivalent vaccine, which is of significant importance in the context of the ongoing epidemic of Omicron variants now globally prevalent.

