3. POST-MONTH 6 STAGE : to assess the relative risk of symptomatic COVID-19 and of severe COVID-19 after the Month 6 dose in Group 1 (PLWH who are SARS-CoV-2 negative at baseline) and Group 2 (PLWH who are SARS-CoV-2 positive at baseline), separately and combined, among those who received mRNA-1273 at Month 6 vs. those who received mRNA-1273.222 at Month 6, counting endpoints at least 14 days after the Month 6 dose until end of follow up.	COVID-19 and severe COVID-19 as defined for the primary endpoints
4. POST-MONTH 6 STAGE : to assess the relative risk of virologically confirmed symptomatic COVID-19 and of severe COVID-19 after the Month 6 dose in Groups 1 and 3 together (participants who are SARS-CoV-2 negative at baseline regardless of HIV status) and in Groups 2 and 4 together (participants who are SARS-CoV-2 positive at baseline regardless of HIV status), respectively, among those who received mRNA-1273 at Month 6 vs. those who received mRNA-1273.222 at Month 6, counting endpoints at least 14 days after Month 6 dose until the end of follow up.	COVID-19 and severe COVID-19 as defined for the primary endpoints
5. PRE-MONTH 6 & POST-MONTH 6 STAGES : to assess the relative risk of symptomatic COVID-19 and of severe COVID-19 after the Month 6 dose by neutralization phenotype and Spike sequence features of acquired SARS-CoV-2 viruses (sieve analysis) in Groups 1 and 3 together (participants who are SARS-CoV-2 negative at baseline regardless of HIV status) and in Groups 2 and 4 together (participants who are SARS-CoV-2 positive at baseline regardless of HIV status), respectively, among those who received mRNA-1273 at Month 6 vs. those who received mRNA-1273.222 at Month 6, counting endpoints starting 1 day after dose 1, 14 days after the last pre-Month6 dose , or 14 days after Month 6 dose until the end of follow up.	COVID-19 and severe COVID-19 as defined for the primary endpoints; neutralization phenotypes and viral genotypic characteristics of SARS-CoV-2 at diagnosis.

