For all primary and secondary comparisons and a subset of exploratory analyses, the time origin for time-to-event COVID-19 or severe COVID-19 endpoints is either the day of or 13 days after the Month 6 vaccination visit, counting events either starting 1 day or 14 days after the Month 6 vaccination. For a subset of exploratory analyses that will include information from enrollment until Month 12 or Month 18, the time origin is either the date of enrollment or 13 days after the Month 6 vaccination visit, counting events either starting 1 day after enrolment or 14 days after the Month 6 vaccination. The Cox model approach will always use the calendar time scale and the cumulative incidence approach will always use the study time scale. See more details about these two approaches in later sections. These analyses will address the co-primary objectives, key secondary objectives and exploratory objectives specified in the protocol (Version 8.0).

Different analyses specify different time origins for the COVID-19 or severe COVID-19 (if applicable) time-to-event T ; the endpoint date is always the same: the date of the first occurrence of COVID-19 or severe COVID-19 endpoint after the corresponding time-origin and up to the date of Month 12 or Month 18 visit. The failure time T is right-censored by the first event of receipt

of outside vaccination, loss to follow-up, or reaching the upper window of the Month 12 (for the Month 12 analyses) or Month 18 visit (for the final analyses), whichever occurs first.

5 SARS-CoV-2 status at baseline and at Month 6

This section defines baseline and Month 6 SARS-CoV-2 statuses, as well as recent SARS-CoV-2 infection status at Month 6 for the pre- & post-M6 stage combined analyses and for the post-M6 stage analyses. These variables will be used as a stratification variable to define different analysis groups, evaluated as a covariate to adjust for prior exposure, and/or as a potential effect modifier in various analyses.

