Calendar-time-based Cox proportional hazards models will be employed to estimate the hazard ratio (HR) between the bivalent vs. monovalent randomized arms. The model will be stratified by the 4 study groups and region (RSA vs. other), thus allowing for a different baseline hazard for each of the $4 \times 2 = 8$ strata. Since the comparison is between randomized groups, the main analysis will only adjust for a small number of covariates that are deemed important or known to be associated with COVID-19 risk to increase efficiency in statistical inference. In particular, sex-assigned-at-birth (Female vs. Male) and baseline history of TB (yes vs. no) were found associated with CDC endpoints in Part A analyses, and having had a recent infection is expected to be associated with COVID-19 risk. Therefore, sex-assigned-at-birth, history of TB at Month 6, and recent SARS-CoV-2 infection status at Month 6 (see definition in Section 5) will be adjusted for in all primary and secondary analyses comparing randomized bivalent vs. monovalent boost arms. These analyses will also be repeated within people who live with HIV (PLWH) and HIV-negative participants, separately. For analyses among PLWH, CD4 counts (\leq vs. > 500 cells/mm 3 at Month 6) and HIV viral load (detectable vs. not detectable at Month 6) will be further adjusted for in

addition to sex assigned at birth, history of TB and recent infection status. For analyses among HIV-negative participants, a subset of the covariates maybe considered to avoid data sparsity, with recent SARS-CoV-2 status as the leading covariate to consider. Specifically, for Cox regression among HIV-negative participants (PLWoH), we will not adjust for TB status due to data sparsity.

We also make comparisons of covariate-adjusted cumulative incidence curves for each comparison arm. We provide a full description of the covariate-adjustment strategies in Section 11.3.

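### The SAP has no randomised bivalent-versus-monovalent comparison within baseline SARS-CoV-2 groups and no arm-by-status interaction, although protocol secondary objectives 3 and 4 call for the within-group comparison

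*SAP*

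**What the plan says.** **Protocol.** Secondary objective 3 asks for the booster comparison in Group 1 and "Group 2 (PLWH who are SARS-CoV-2 positive at baseline), separately and combined, among those who received mRNA-1273 at Month 6". Secondary objective 4 asks for it "in Groups 1 and 3 together (participants who are SARS-CoV-2 negative at baseline regardless of HIV status) and in Groups 2 and 4 together", each in its own right. Section 6.4.3 adds that a relative risk between arms is to be estimated inside each group, and leaves details to the SAP. Section 6.3 says the sizes of Groups 1 and 2 were driven partly by the randomised Month 6 comparison within each group. Section 2.1 gives the reason: post-Month 6 follow-up should show "whether individuals with hybrid versus vaccine-only immunity have different responses to the bivalent vaccine".

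**SAP.** Section 4 states: "These analyses will address the co-primary objectives, key secondary objectives and exploratory objectives specified in the protocol (Version 8.0". Section 5 says SARS-CoV-2 status variables may serve as stratifiers, as covariates, or "as a potential effect modifier in various analyses". For the randomised contrast, Section 7.1 names one subgroup split: "These analyses will also be repeated within people who live with HIV (PLWH) and HIV-negative participants, separately". Table 2 carries that split as Secondary III–V, with the population of III and IV given as "PLWH/PLWoH randomized to monovalent or bivalent under Protocol Version 6 (RM6". In Section 11.4.1, study group and region define separate baseline hazards in model (4), but the treatment effect is a single coefficient.

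**The concern.** Followed as written, the SAP leaves undone a randomised comparison that the protocol lists as a secondary objective. A single coefficient averages the booster effect over participants with and without prior infection and cannot show whether it differs between them. The protocol treats that difference as important. The two kinds of participant also differed in risk before Month 6: protocol section 2.1 reports annual COVID-19 incidence in PLWH of 7.1% without and 2.2% with evidence of prior infection.

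The omission is avoidable. Randomisation was stratified by HIV status and SARS-CoV-2 serostatus (protocol 6.8) and blocked within study group for those boosted under version 6 (SAP Section 2), so a within-group comparison is protected by the design. If it is added only after results are known, it becomes post hoc.

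**Working it through.** **1. Coverage, objective by objective.**

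| Protocol requirement | SAP row |
|---|---|
| Objective 3, Groups 1 and 2 combined | Secondary III, PLWH part (also V, in FPP) |
| Objective 3, Group 1 alone | none |
| Objective 3, Group 2 alone | none |
| Objective 4, Groups 1+3 | none |
| Objective 4, Groups 2+4 | none |

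Primary I–IV and Secondary I–II are overall; Secondary III–V are split by HIV. Exploratory I and II compare boosters in FM6, again overall or by HIV. No arm-by-status term appears in Section 11.

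**2. What the exploratory rows give.** VI and VII estimate hybrid against vaccine immunity within monovalent and within bivalent recipients. Writing h for hazard, H/V for hybrid/vaccine immunity and b/m for booster:

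[h(H,b)/h(V,b)] ÷ [h(H,m)/h(V,m)] = [h(H,b)/h(H,m)] ÷ [h(V,b)/h(V,m)]

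Dividing VII by VI therefore yields the ratio of booster effects, but not the booster hazard ratio in either stratum. III and IV allow the same step from enrolment. The interaction in model (6) is between immunity group and having been boosted, not which booster was given.

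**3. The plan's own figures.** Protocol Table 6-2, post-Month 6, uses a two-sided exact binomial test at 0.05. Conditioning on the tabulated events with p = RR/(1+RR) against 0.5:

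| Events | RR | Stated | Reproduced |
|---|---|---|---|
| 110 | 1.5 | 54% | 54.1% |
| 106 | 2.0 | 93% | 92.9% |
| 91 | 2.0 | 87% | 87.4% |
| 90 | 2.5 | 99% | 98.7% |
| 76 | 2.0 | 78% | 78.1% |
| 75 | 2.5 | 96% | 96.2% |

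All six rows reproduce. I use 76, 91 and 106 events below.

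**4. Share of events in Groups 1+3 (an assumption).** The documents do not give the group mix among the roughly 4000 boosted under version 6, nor post-Month 6 rates by status.
- Planned sizes, equal rates: (4200+1000)/15,600 = 33%.
- Planned sizes, pre-Month 6 interim rates (7.1, 2.2, 5.8 and 1.5% in Groups 1–4): (4200×7.1 + 1000×5.8)/(4200×7.1 + 8400×2.2 + 1000×5.8 + 2000×1.5) = 35,620/57,100 = 62%.

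**5. Precision at 91 events.** SE of a log hazard ratio = 2/√d. Interaction SE = √(4/d₁ + 4/d₂).

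| Negative share | d₁/d₂ | SEs | 95% CI factors | Interaction SE |
|---|---|---|---|---|
| 33% | 30/61 | 0.36, 0.26 | 2.0, 1.7 | 0.44 |
| 50% | 45.5/45.5 | 0.30, 0.30 | 1.8, 1.8 | 0.42 |
| 62% | 57/34 | 0.265, 0.342 | 1.7, 2.0 | 0.43 |

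The first interaction SE is 0.445 before rounding. The result barely depends on the assumed share.

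**6. Power.** Per stratum, true RR 2.0: Φ(ln 2 × √d/2 − 1.96). With the share from 33% to 60%:
- 76 events: 41–65% negative, 69–48% positive.
- 106 events: 54–79% negative, 83–62% positive.

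For a twofold ratio of effects, Φ(ln 2/SE − 1.96) gives 30–33% at 76 events, 34–38% at 91 and 39–43% at 106. The ratio detectable with 80% power is about 3.6–3.9 at 76 events and 3.0–3.2 at 106.

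**7. The SAP's event rules (Section 7.1).** At 76 events the strata hold about 25/51 to 47/29, above the 20-event floor; three covariates need 15. Within PLWH the five covariates need 25. Group 2 at interim rates has 76 × (8400×2.2)/57,100 = 24.6 events; Group 1 at equal rates has 76 × 4200/15,600 = 20.5. Either could miss the rule with full adjustment, and Month 12 counts will be lower.

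**The case against.** The strongest reply is that the question has not been dropped. The exploratory analyses reach it through the ratio in step 2, the PLWH row delivers the combined part of objective 3, and protocol 6.4.3 still prespecifies a within-group estimate. The SAP claims only key secondary objectives and describes SARS-CoV-2 status only as a potential effect modifier.

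Much of this stands, and it rules out four stronger readings that a reader might infer:
- *That the question is never analysed.* Exploratory III/IV and VI/VII bear on it.
- *That the SAP swapped SARS-CoV-2 status for HIV status.* PLWH is Groups 1 and 2 combined, which objective 3 requests.
- *That Section 5 commits to an effect-modification analysis.* Its wording is permissive.
- *That the pooled hazard ratio mainly describes participants without prior infection.* The 62% share carries pre-Month 6 rates and planned sizes into a later, boosted cohort. Study groups also rest on point-of-care serology alone, and SAP Table 1 gives a 0.32 probability of positive central serology among point-of-care negatives. If that 32% applied to Groups 1 and 3 and the interim rates followed three-test status, naive participants would supply (2856×7.1 + 680×5.8)/(2856×7.1 + 9744×2.2 + 680×5.8 + 2320×1.5) = 24,222/49,138 = 49% of events.

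The reply does not fill the gap. The indirect route covers PLWH only, so it cannot meet objective 4. FM6 mixes in monovalent recipients boosted before version 6, outside randomisation. VI/VII drop AG2.1 participants with a recent infection. No test compares the two hazard ratios, and Section 8.2 says these analyses may not all be done for the primary publication. The protocol's estimate needs an SAP row to be carried out.

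Low power is also a fair objection. It bears on how results are presented, not on whether a protocol objective is estimated.

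**Conclusion.** The concern holds as an omission. The SAP has no direct randomised estimate for objective 3 (Groups 1 and 2 separately) or for any of objective 4, and no arm-by-status interaction. The primary comparison remains valid.

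The restored analysis would be one of estimation. At 91 events each stratum's 95% interval spans a factor of about 1.7 to 2.0 either side of the hazard ratio, the interaction SE is 0.42–0.45, and power for a twofold interaction is about 30–43% across 76 to 106 events. These figures rest on Table 6-2 event totals, equal allocation and an assumed negative share of 33–62%. The coverage finding depends on none of them.

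**What to change.** - **Rows.** Add to SAP Table 2 a secondary analysis using model (4) in RM6, counting from Day 14, within Groups 1+3 and Groups 2+4, and within Groups 1 and 2 separately.
- **Stratum definition.** Use study group, the point-of-care factor used in randomisation, as the main definition. Repeat with three-test baseline status as a sensitivity analysis, because protocol 6.2 reserves the anti-spike result for assignment.
- **Interaction.** Add one arm-by-stratum term. Under the study-group definition its main effect is already absorbed by the stratified baseline hazard; the sensitivity model needs status entered as well. Report both hazard ratios and the interaction interval.
- **Event rules.** Apply the existing 20-event and five-events-per-covariate rules in each stratum, reducing covariates where needed.
- **Labelling.** State that this is estimation, that the event share is assumed, and what power to expect.

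The cost is a few table rows and one model term, with no new data. The downside is wide intervals in both strata.
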